#### 18.4. Vital Signs

The following Vital Signs measurements will be reported for this study:

- Sitting / Supine Systolic Blood Pressure (mmHg)
- Sitting / Supine Diastolic Blood Pressure (mmHg)
- Sitting / Supine Pulse Rate (bpm)
- Respiratory Rate (breaths/min)
- Body Temperature (° C)

Vital signs parameters will be summarized using descriptive statistics at each analysis visit. Abnormalities will be presented as cross-tabulations of the abnormality at each post-baseline analysis visit.

All datapoints obtained after informed consent up to 60 days after IMP discontinuation or database cutoff will be considered.

The following summaries will be provided for vital signs data:

- Vital signs parameters will be summarized using descriptive statistics at each analysis visit.
- Abnormalities will be presented as cross-tabulations of the abnormality at each postbaseline analysis visit and at
  the worst-case analysis visit versus the baseline abnormality.
- All vital signs data will be listed, but only for participants with any postbaseline abnormality.

#### 18.4.1. Vital Signs Abnormal Criteria

Abnormal quantitative Vital Signs measurements will be identified in accordance with the following predefined abnormal criteria.

Variable	Unit	Low	Normal	High
SBP	mmHg	< 90	90-150	> 150
DBP	mmHg	< 45	45 – 90	> 90
Heart rate	Bpm	< 40	40 – 100	> 100

Document:

Author:

Version Number: V2.0

Version Date: 31JAN2024

Template No.: CS\_TP\_BS016 Revision 7 Reference: CS\_WI\_BS005

Effective Date: 01Nov2021

Statistical Analysis Plan

Page 71 of 78

Variable	Unit	Low	Normal	High
Body temperature	°C	< 35.8	35.8 – 37.5	> 37.5

Note: For the worst-case analysis visits, as defined in Section 6.4, an additional category "low + high" is defined if there are both low and high postbaseline values.

#### 18.5. Physical Examination

A complete physical examination will include, at a minimum, assessments of the musculoskeletal, gastrointestinal, pulmonary, cardiovascular, respiratory, and neurological systems, and general appearance, skin, and lymph nodes. Additionally, physical examinations will be performed to assess ESSDAI, as appropriate. Height and weight will also be measured.

Brief physical examination will include weight, assessments of gastrointestinal, pulmonary, cardiovascular, and respiratory systems; and general appearance.

All datapoints obtained after informed consent up to 60 days after IMP discontinuation or database cutoff will be considered. Physical examination abnormalities will be listed.

#### 19. PHARMACOKINETIC ANALYSIS

PK analyses will be performed in the PKAS.

At IMP administration visits, PK blood samples will be collected predose (within the 2 hours before IMP infusion).

A listing of PK blood sample collection times, derived sampling time deviations, and concentrations will be provided. A subject listing of all concentration-time data will be presented by study day and scheduled time point.

Serum concentrations will be summarized using descriptive statistics for efgartigimod. The pharmacokineticist will determine a strategy for dealing with data affected by protocol deviations or events which may impact the quality of PK concentration data on a case-by-case basis with input from the study physician, as needed. Examples of protocol deviations or events include, but may not be limited to the following:

When a predose sample is taken after IMP administration.

Document:
Author:

Version Number: V2.0
Version Date: 31JAN2024

Template No.: CS\_TP\_BS016 Revision 7 Reference: CS\_WI\_BS005

Effective Date: 01Nov2021

Statistical Analysis Plan

Page 72 of 78

- When the most recent IMP administration before the scheduled predose PK sample or any other scheduled PK sample (ie, week 24 sample) is missed (not applicable for Day 1).
- Samples are collected following the occurrence of incomplete or incorrect dosing for the most recent prior dose
  administration Any administration. Any event related to sample collection, handling and storage that affects the
  integrity of the samples and/or the bioanalytical results.
- When predose PK samples are taken outside the visit windows.
  - o The study visit windows are  $\pm 2$  days

In the case of an important protocol deviation or event, the PK data collected may be excluded from the summaries and a reason for the exclusion of the data point will be added in the appropriate listing.

Figures of geometric mean concentration-time data (±SD on linear plot, as appropriate) may be presented for efgartigimed on linear and semi-logarithmic scales. Individual participant concentration-time data will be graphically presented on linear and semi-logarithmic scales. Individual concentrations which are BLQ will be displayed as zero in the graphic presentations on linear scale; but will not be plotted on semi-logarithmic scale. Means which fall below the BLQ will also be displayed as zero in the graphic presentations on the linear scale, but will not be plotted on semi-logarithmic scale.

The strategy for the population PK analysis and any related exposure-response modeling utilizing the efgartigimod concentration and IgG data collected from this study will be outlined separately in the PK analysis plan.

#### **APPENDIX 1. PROGRAMMING CONVENTIONS FOR OUTPUTS**

#### **IQVIA Output Conventions**

Outputs will be presented according IQVIA Standard conventions. Kindly refer to output templates for additional information.

#### **Dates & Times**

Depending on data available, dates and times will take the form yyyy-mm-ddThh:mm:ss.

#### **Presentation of Treatment Groups**

For outputs, treatment groups will be represented as follows and in the given order:

Treatment Group for Tables, Listings and Figures		
Efgartigimod		
Placebo		

In the demographics and analysis, an overall total will be added to summarize all participants over treatments. Overall totals will be shown last.

Document:

Author:

Version Number:

V2.0

Version Date:

31JAN2024

Template No.: CS TP BS016 Revision 7 Reference: CS WI BS005

Effective Date: 01Nov2021

Statistical Analysis Plan

Page 74 of 78

#### Listings

All listings will be ordered by the following (unless otherwise indicated in the template):

- Randomized treatment group (or treatment received if it's a safety output), first by active dose [by ascending dose group] and then control/ placebo
- Center-participant ID
- Date (where applicable)
- For listings where non-randomized participants are included, these will appear in a category after the randomized treatment groups labeled 'Not Randomized'

Document:

Author:

Version Number: Version Date:

V2.0

31JAN2024

Template No.: CS\_TP\_BS016 Revision 7 Reference: CS WI BS005

Effective Date: 01Nov2021

Statistical Analysis Plan

Page 75 of 78

#### **APPENDIX 2.** TOXICITY GRADES

The table below shows how the CTCAE, v5.0: 27 Nov 2017 will be implemented in the analysis.

Parameter	Unit	Grade 1	Grade 2	Grade 3	Grade 4
Alanine amino transferase		>1-3 *ULN	>3-5 *ULN	>5-20 *ULN	>20 *ULN
Albumin	g/L	<lln-30< td=""><30-20	<20	-	</lln-30<>	<30-20	<20	-
	g/dL	<lln-3< td=""><3-2	<2	-	</lln-3<>	<3-2	<2	-
Alkaline phosphatase		>1.0-2.5 *ULN	>2.5-5.0 *ULN	>5.0-20.0 *ULN	>20.0 *ULN
Aspartate amino transferase		>1-3 *ULN	>3-5 *ULN	>5-20 *ULN	>20 *ULN
Bilirubin (total)		>1.0-1.5 *ULN	>1.5-3.0 *ULN	>3.0-10.0 *ULN	>10.0 *ULN
Calcium (ionized) low	mmol/L	<lln-1.0< td=""><1.0-0.9	<0.9-0.8	<0.8	</lln-1.0<>	<1.0-0.9	<0.9-0.8	<0.8
	mg/dL	<lln-4.0< td=""><4.0-3.6	<3.6-3.2	<3.2	</lln-4.0<>	<4.0-3.6	<3.6-3.2	<3.2
Calcium (ionized)	mmol/L	>ULN-1.5	>1.5-1.6	>1.6-1.8	>1.8
high	mg/dL	>ULN-6.0	>6.0-6.4	>6.4-7.2	>7.2
Calcium (corrected)	mmol/L	<lln-2.00< td=""><2.00-1.75	<1.75-1.50	<1.50	</lln-2.00<>	<2.00-1.75	<1.75-1.50	<1.50
low	mg/dL	<lln-8< td=""><8-7	<7-6	<6	</lln-8<>	<8-7	<7-6	<6
Calcium (corrected)	mmol/L	>ULN-2.9	>2.9-3.1	>3.1-3.4	>3.4
high	mg/dL	>ULN-11.5	>11.5-12.5	>12.5-13.5	>13.5
Cholesterol	mmol/L	>ULN-7.75	>7.75-10.34	>10.34-12.92	>12.92
	mg/dL	>ULN-300	>300-400	>400-500	>500
Creatine kinase		>1.0-2.5 *ULN	>2.5-5.0 *ULN	>5.0-10.0 *ULN	>10.0 *ULN
Creatinine		>1.0-1.5 *ULN	>1.5-3.0 *ULN	>3.0-6.0 *ULN	>6.0 *ULN
Glucose (fasting) low	mmol/L	<lln-3.0< td=""><3.0-2.2	<2.2-1.7	<1.7	</lln-3.0<>	<3.0-2.2	<2.2-1.7	<1.7
	mg/dL	<lln-55< td=""><55-40	<40-30	<30	</lln-55<>	<55-40	<40-30	<30
Lipase		>1.0-1.5 *ULN	>1.5-2.0 *ULN	>2.0-5.0 *ULN	>5.0 *ULN
Potassium low	mmol/L	-	<lln-3.0< td=""><3.0-2.5	<2.5	</lln-3.0<>	<3.0-2.5	<2.5
	mEq/L	-	<lln-3.0< td=""><3.0-2.5	<2.5	</lln-3.0<>	<3.0-2.5	<2.5
Potassium high	mmol/L	>ULN-5.5	>5.5-6.0	>6.0-7.0	>7.0

Document:

Author:

Version Number:

V2.0

Version Date:

31JAN2024

Template No.: CS\_TP\_BS016 Revision 7

Reference: CS\_WI\_BS005

Effective Date: 01Nov2021

Statistical Analysis Plan

Page 76 of 78

Parameter	Unit	Grade 1	Grade 2	Grade 3	Grade 4
	mEq/L	>ULN-5.5	>5.5-6.0	>6.0-7.0	>7.0
Sodium low	mmol/L	<lln-130< td="">-	<130-120	<120	</lln-130<>	-	<130-120	<120
	mEq/L	<lln-130< td="">-	<130-120	<120	</lln-130<>	-	<130-120	<120
Sodium high	mmol/L	>ULN-150	>150-155	>155-160	>160
	mEq/L	>ULN-150	>150-155	>155-160	>160
CD4 count	giga/L	<lln-0.50< td=""><0.50-0.20	<0.20-0.05	<0.05	</lln-0.50<>	<0.50-0.20	<0.20-0.05	<0.05
	counts/m m 	<lln-500< td=""><500-200	<200-50	<50	</lln-500<>	<500-200	<200-50	<50
Lymphocytes	giga/L	<lln-0.80< td=""><0.80-0.50	<0.50-0.20	<0.20	</lln-0.80<>	<0.80-0.50	<0.50-0.20	<0.20
(absolute count) low	counts/m m 	<lln-800< td=""><800-500	<500-200	<200	</lln-800<>	<800-500	<500-200	<200
Lymphocytes	giga/L	-	>4-20	>20	-
(absolute count) high	counts/m m 	-	>4000-20000	>20000	-
Neutrophils (absolute	giga/L	<lln-1.5< td=""><1.5-1.0	<1.0-0.5	<0.5	</lln-1.5<>	<1.5-1.0	<1.0-0.5	<0.5
count) low	counts/m m 	<lln-1500< td=""><1500-1000	<1000-500	<500	</lln-1500<>	<1500-1000	<1000-500	<500
Platelets	giga/L	<lln-75< td=""><75-50	<50-25	<25	</lln-75<>	<75-50	<50-25	<25
	counts/m m 	<lln-75000< td=""><75000-50000	<50000-25000	<25000	</lln-75000<>	<75000-50000	<50000-25000	<25000
White blood cells	giga/L	<lln-3< td=""><3-2	<2-1	<1	</lln-3<>	<3-2	<2-1	<1
	counts/m m 	<lln-3000< td=""><3000-2000	<2000-1000	<1000	</lln-3000<>	<3000-2000	<2000-1000	<1000

CTCAE= Common Terminology Criteria for Adverse Events; LLN=lower limit of normal; ULN=upper limit of normal

Note: In case ULN/LLN is higher/lower than the upper/lower limit of grade 1 (or even higher grades), ULN/LLN will be ignored and only the fixed values of CTCAE will be considered.

Values within normal ranges will be presented as Grade 0 for Toxicity outputs.

Document:
Author: Version Number: V2.0

Version Date: 31JAN2024

Template No.: CS\_TP\_BS016 Revision 7 Reference: CS\_WI\_BS005

Effective Date: 01Nov2021

Statistical Analysis Plan

Page 77 of 78

## APPENDIX 3. ALGORITHM FOR PRIOR / CONCOMITANT MEDICATIONS

START DATE	STOP DATE	ACTION
Known Known		If stop date < study med start date, assign as prior
		If stop date >= study med start date, assign as concomitant
	Partial	If only day is missing: compare Month and year from start and stop date
		based on rule described below:
		If stop date < study med start date, assign as prior
		If stop date >= study med start, assign as concomitantOr else, assign as
		Concomitant and Prior.
		If day and month are missing please compare the year and implement rules
		described above.
	Missing	Assign as concomitant and prior.
Partial	Known	If stop date < study med start date, assign as prior
		If stop date >= study med start date, assign as concomitant
	Partial	If only day is missing: compare Month and year from start and stop date
		based on rule described below:
		If stop date < study med start date, assign as prior
		If stop date >= study med start, assign as concomitantOr else, assign as
		Concomitant and Prior.
		If day and month are missing please compare the year and implement rules
		described above.
	Missing	Assign as concomitant and prior.

Document:

Author: Version Number: V2.0

Version Date: 31JAN2024

Template No.: CS\_TP\_BS016 Revision 7 Reference: CS\_WI\_BS005

Effective Date: 01Nov2021

Statistical Analysis Plan

Page 78 of 78

START DATE	STOP DATE	ACTION
Missing	Known	If stop date < study med start date, assign as prior
		If stop date >= study med start date, assign as concomitant
	Partial	If only day is missing: compare Month and year from start and stop date
		based on rule described below:
		If stop date < study med start date, assign as prior
		If stop date >= study med start, assign as concomitantOr else, assign as
		Concomitant and Prior.
		If day and month are missing please compare the year and implement rules
		described above.
	Missing	Assign as concomitant and prior.

Document:
Author:

Version Number: V2.0

Version Date: 31JAN2024

Template No.: CS\_TP\_BS016 Revision 7 Reference: CS\_WI\_BS005

Effective Date: 01Nov2021

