#### 11. PRIOR AND CONCOMITANT THERAPY

All therapies will be coded using WHO-DRUG and presented for the SAF. Anatomical Therapeutic Chemical (ATC) selection is performed. ATC coding up to level 4 is available in the clinical database.

See Appendix 3 for handling of partial and missing dates for medications.

In the case where it is not possible to define a medication as prior or concomitant, the medication will be classified by the worst case; i.e. concomitant.

Based on their start and stop dates, therapies will be allocated to 1 or both of the following categories:

- 'Prior' therapies are therapies which strictly started prior to the first dose date of IMP.
- 'Concomitant' therapies are therapies which are taken on or after the first dose date of IMP.

If the start and/or stop date is incomplete or missing, the therapy will be allocated to both categories unless the available parts of the start and/or stop date provide evidence that the therapy was not administered during the specific period.

Prior and concomitant therapies will be tabulated by ATC class (level 1 and 3) and generic term.

Certain medications or treatments are not permitted during the periods listed in Table 4 of protocol.

All prior and concomitant therapies will be listed.

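### SAP Appendix 3 sets prior/concomitant status from the stop date alone, so two kinds of therapy get the wrong prior label under the definition in SAP Section 11

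*SAP*

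**What the plan says.** SAP Section 11 gives the definitions. Prior "therapies are therapies which strictly started prior to the first dose date of IMP". Concomitant therapies are those taken on or after that date. The two are not exclusive: "Based on their start and stop dates, therapies will be allocated to 1 or both of the following categories". If a date is incomplete or missing, the therapy goes into both categories "unless the available parts of the start and/or stop date provide evidence that the therapy was not administered during the specific period". Section 11 then points to Appendix 3 for the handling of partial and missing dates.

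SAP Appendix 3 is a grid of start-date status (known, partial, missing) by stop-date status (known, partial, missing). Its actions are:

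- **Known stop before first dose:** prior.
- **Known stop on or after first dose:** "If stop date >= study med start date, assign as concomitant".
- **Partial stop:** the same two tests on the available date parts, with a fallback to "assign as Concomitant and Prior".
- **Missing stop:** both labels.

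The three start-date blocks carry the same actions. The partial-stop rows mention comparing start and stop dates, but the tests that follow compare only the stop date with the start of study medication.

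**The concern.** A rule that uses only the stop date cannot reproduce a definition that rests on the start date. Two ordinary records show this. A drug begun on study with no stop date is filed partly as prior, although its start date proves otherwise. A background drug begun before dosing and stopped on study is not filed as prior at all.

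At stake is what the prior-therapy tables show by arm. The protocol permits some background treatment, for example limited oral corticosteroids, anticholinergics and salivary or lacrimal stimulants (Section 6.9, Table 4), and certain antimalarials or conventional DMARDs (Section 5.2, criterion 20). Randomisation is stratified only by screening IgG (Protocol Section 6.3). The readable part of the baseline list in SAP Section 9 names no background therapy, so the Section 11 tables are the visible planned summary of it. Under Appendix 3 the prior table can include treatment begun after randomisation, which may depend on arm, and can omit real background treatment that was stopped on study.

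**Working it through.** The plan gives no figure to reproduce here. The check applies both sets of rules to the same records.

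**Inputs.** Section 11: prior if the start is before first dose, or missing and not ruled out; concomitant if taken on or after first dose, or if a missing stop does not rule that out. Appendix 3: stop before first dose gives prior; stop on or after gives concomitant; stop missing gives both.

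| Start | Stop | Section 11 | Appendix 3 | Prior label agrees |
|---|---|---|---|---|
| Before first dose | Before | Prior | Prior | Yes |
| Before first dose | On/after | Both | Concomitant | **No** |
| Before first dose | Missing | Both | Both | Yes |
| On/after first dose | On/after | Concomitant | Concomitant | Yes |
| On/after first dose | Missing | Concomitant | Both | **No** |
| Missing | Before | Prior | Prior | Yes |
| Missing | On/after | Both | Concomitant | No, but arguable |
| Missing | Missing | Both | Both | Yes |

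**Two clear errors.**

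1. Known start on or after first dose, stop missing. The start date is evidence that the drug was not used before dosing, so the Section 11 exception removes the prior label. Appendix 3 keeps it.
2. Known start before first dose, known stop on or after it. Section 11 gives both labels and Appendix 3 gives concomitant only. A partial stop date that is clearly on or after first dose gives the same result.

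**A third, arguable mismatch.** With a missing start and an on-study stop, the incomplete-date rule in Section 11 gives both labels. Section 11 also says that a medication that cannot be classified is treated as concomitant, so its own text does not settle this case.

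**Concomitant label.** It agrees in all eight patterns.

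**Size in a table row.** Protocol Section 9.5 plans about 15 + 15 = 30 participants at 2:1, so about 20 on efgartigimod and 10 on placebo. If k participants in an arm are misfiled in a row, the shift is 100 × k/20 or 100 × k/10 percentage points. The documents give no rate for k, so these values are assumed:

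| k | Efgartigimod | Placebo |
|---|---|---|
| 0 | 0 | 0 |
| 1 | 5 | 10 |
| 2 | 10 | 20 |

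**The case against.** The strongest reply is that Section 11 already gives the right answers. It refers to Appendix 3 only for partial and missing dates, so fully dated drugs fall under its own definitions, and its exception for available date parts resolves the drug started on study. This has some force, but it does not remove the conflict. Appendix 3 has its own row for two known dates, and that row produces the second error. The missing-stop row lies within the referred scope and produces the first. The SAP does not say which text prevails, so two programmers could produce different tables.

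Other limits stand:

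- Appendix 3 has no row for ongoing drugs. The first error reaches them only if they are recorded without a stop date.
- Participants are meant to keep their medication unchanged during the study (Protocol Section 6.9), so the second error needs a departure from that. Background therapy that continues with no stop date is labelled correctly as both.
- A background drug stopped on study is still in the concomitant table.

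A reader might infer that the arms' background and added treatment could not be told apart at all. The documents do not support that. Section 11 plans a listing of all prior and concomitant therapies, and Protocol Section 6.9 requires start and end dates to be recorded. Nor do the documents show that background therapy affects every CRESS item.

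**Conclusion.** The point holds as a conflict inside the SAP. For two date patterns, Appendix 3 gives a prior label that contradicts Section 11: one is added wrongly and one is dropped wrongly. The drug started on study is labelled concomitant and prior, not prior alone, so only the extra prior label is wrong.

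A reader might infer that the error reaches the CRESS result or the handling of prohibited medication as an intercurrent event (SAP Table B and Section 14.1.1). It does not. Those concern on-study use, the concomitant label is right, and no visible efficacy or safety analysis uses the prior label.

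The effect is limited to descriptive prior-therapy tables and labels, at about 5 points per misfiled participant on efgartigimod and 10 on placebo. This rests on the planned arm sizes. How many records are affected is unknown, and for ongoing drugs it depends on how they are coded.

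**What to change.** Rewrite the Appendix 3 actions to use both dates:

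- **Prior** if the start date, or its known part, is before first dose or cannot be shown to be on or after it.
- **Concomitant** if the stop date is on or after first dose, is missing or ongoing, or cannot be shown to be before it.
- **Both** when both conditions hold.

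Add one sentence saying that the Section 11 definitions prevail. Under these rules all eight patterns match Section 11 (using its incomplete-date rule for the arguable row): the drug started on study with no stop date becomes concomitant only, and the background drug stopped on study becomes both.

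A separate table of therapies newly started on study would be a useful option, but this correction does not require it.

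The cost is a short SAP wording change and a small programming change, with no new data. The SAP modification history shows that version 3.0 already corrected a slip in a CRESS component in the same way. If the SAP can no longer be changed, Protocol Section 9 provides for later changes in planned analysis to be described in the CSR.
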